11.6. Appendix 6: Derived and Transformed Data

(Placebo) Run-In Start and Stop Dates

- Placebo run-in start date = Start date of (placebo) study treatment recorded for the run-in period. If the recorded start dates for the two study drug containers differ, then select the earlier start date.
- Placebo run-in stop date = End date of (placebo) study treatment recorded for the run-in period. If the recorded stop dates for the two study drug containers differ, then select the later stop date.

Note: a subject with a nonmissing placebo run-in start date will be considered as included in the Placebo Run-in Phase.

Randomization Date

- Randomization date is the randomization telephone call in date which is recorded in the eCRF. This date is defined here for completeness and no derivations are made.

Note: a subject with a nonmissing randomization number recorded in eCRF will be considered Randomized.

(Double-Blind) Treatment Start and Stop Dates

- Treatment start date = Start date of study treatment recorded for the (double-blind) treatment period. If the recorded start dates for the two study drug containers differ, then select the earlier start date.
- Treatment stop date = Stop date of study treatment recorded for the (double-blind) treatment period. If the recorded stop dates for the two study drug containers differ, then select the later stop date.

Study Drug Exposure and Compliance

 As explained in the protocol: 
 -Dutasteride study treatment is dispensed as capsules within bottles. -Tamsulosin study treatment is dispensed as tablets within blister packs. 
Within this RAP, the following general terms are used for exposure and compliance:
 
 ---"Pill" refers to a capsule or a tablet ---"Container" refers to a bottle or a blister pack. 
 Study drug exposure (in days) is number of days between (double-blind) treatment start date and (double-blind) treatment stop date, both days inclusive (i.e. Study drug exposure =Treatment Stop Date – Treatment Start Date +1). Number of pills consumed during the study is defined for double-blind period as total number of pills dispensed (sum over all containers dispensed) minus total number of pills returned (sum over all containers dispensed) minus total number of pills lost or wasted (sum over all containers dispensed). If any of the containers is not returned or number of pills returned or wasted is missing for any container, number of pills consumed during the study is missing. Overall study drug compliance is defined for double-blind period as $100 * \text{Number of Pills Consumed} / \text{Number of Pills Prescribed}$. Number of Pills Prescribed = $2 * \text{Study Drug Exposure}$, since the protocol prescribes that subjects consume 2 pills for each day a subject is on treatment (one pill of Placebo or Dutasteride, and one pill of Tamsulosin). Overall study drug compliance is missing if either the number of pills consumed during the study or the study drug exposure is missing. Compliance by study drug component: Study drug compliance by component will be output for: 
 -Placebo + Tam 0.2mg for each of the two components: Placebo and Tam 0.2mg --Dut 0.5mg + Tam 0.2mg for each of the two components: Dut 0.5mg and Tam 0.2mg Compliance is defined as $100 * \text{Number of Pills Consumed} / \text{Number of Pills Prescribed}$, where the only pills considered are those for a specific(e.g. Tamsulosin). Number of Pills Prescribed = Study Drug Exposure, since the protocol prescribes that subjects consume 1 pill of any study drug component (e.g. Tamsulosin) for each day a subject is on treatment.
Baseline Date

 A subject's baseline date will be the latest non-missing value of either (double-blind) treatment start date or randomization date. Baseline date will be used in the derivation of study day values and Baseline Values. 'Baseline date' may differ from the Visit 2 (Baseline Visit) date recorded in eCRF.
Baseline Value

 For purposes of data analyses, the subject's baseline value of an assessment will be defined as the latest assessment on or before the Baseline Date.
Change and % Change from Baseline

 Change from Baseline = Post-baseline Value – Baseline % Change from Baseline = $100 \times [(\text{Post-baseline Value} - \text{Baseline}) / \text{Baseline}]$

Study Day																				
Study Day is calculated as the number of days from Baseline Date:																				

 • Reference Date = Missing → Study Day = Missing • Reference Date < Baseline Date → Study Day = Reference Date – Baseline Date • Reference Date ≥ Baseline Date → Study Day = Reference Date – (Baseline Date) + 1 																				
Cut-off Dates																				
-Month k Cut-off Date (for k= 3, 6, 9, 12, 15, 18, 21, 24): The maximum of [Month k clinic visit date, Month k lab visit date, Baseline Date + (k * 91/3)].																				
Time Since LUTS First Noted (in years)																				
-Time Since LUTS First Noted = Baseline Date minus Date LUTS First Noted by Patient / 365																				
Time Since BPH Clinical Diagnosis (in years)																				
-Time Since BPH Diagnosis = Baseline Date minus Date of BPH Clinical Diagnosis / 365																				
Age																				
Only year of birth is collected in the eCRF. For purposes of calculating age for a given subject, date of birth will be defined as June 30 th of the corresponding year of birth. Age is calculated in terms of Screening (Visit 1b) date and output as a truncated integer. Age categories include <65, ≥65, <75, and ≥75 years.																				
Body Mass Index (BMI) (kg/sq m)																				
BMI = Weight (kg) / [Height (m)] ²																				
Race / Ethnicity																				
Race / ethnicity will be determined based on a subject's reported ethnicity and geographic ancestry as defined in the following table.																				

  
 Race / Ethnicity	
 
 	Asian	White (But Not Hispanic)	Hispanic	Other	
   
 Ethnicity	Not Hispanic or Latino	Not Hispanic or Latino	Hispanic or Latino	Not Hispanic or Latino	
 
 Geographic Ancestry	 Any combination of (restricted to the categories below only): 
 -Asian – East Asian Heritage -Asian – Japanese Heritage -Asian - South East Asian Heritage -Asian – Central / South Asian Heritage 	 Any combination of (restricted to the below categories only): 
 -White – Arabic/ North African Heritage -White – White/ Caucasian/ European Heritage 	Any combination	Any combination not considered 'Asian' or 'White (But Not Hispanic)'	
  
	Race / Ethnicity						Asian	White (But Not Hispanic)	Hispanic	Other	Ethnicity	Not Hispanic or Latino	Not Hispanic or Latino	Hispanic or Latino	Not Hispanic or Latino	Geographic Ancestry	Any combination of (restricted to the categories below only): 
 -Asian – East Asian Heritage -Asian – Japanese Heritage -Asian - South East Asian Heritage -Asian – Central / South Asian Heritage 	Any combination of (restricted to the below categories only): 
 -White – Arabic/ North African Heritage -White – White/ Caucasian/ European Heritage 	Any combination	Any combination not considered 'Asian' or 'White (But Not Hispanic)'
Race / Ethnicity																				
	Asian	White (But Not Hispanic)	Hispanic	Other																
Ethnicity	Not Hispanic or Latino	Not Hispanic or Latino	Hispanic or Latino	Not Hispanic or Latino																
Geographic Ancestry	Any combination of (restricted to the categories below only): 
 -Asian – East Asian Heritage -Asian – Japanese Heritage -Asian - South East Asian Heritage -Asian – Central / South Asian Heritage 	Any combination of (restricted to the below categories only): 
 -White – Arabic/ North African Heritage -White – White/ Caucasian/ European Heritage 	Any combination	Any combination not considered 'Asian' or 'White (But Not Hispanic)'																
IPSS (total score)																				
IPSS (total score) = Sum of IPSS individual questions 1 – 7. Reference Section 7.1.1 for imputation procedure.																				
Prostate Volume																				
Prostate Volume = $\pi/6$ (Anteroposterior Width x Cephalocaudal Width x Transverse Width)																				

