6.6. Investigational Product Discontinuation, Exposure, and Compliance

Reasons for investigational product discontinuation are recorded in the eCRF and may differ from a subject's study discontinuation reason. A tabular summary will be produced for number and percentage of subjects who prematurely discontinued investigational product. Summaries will be produced overall and by reason, and will be output by treatment group and total. For this summary, the percentages are calculated using the ITT population as the denominator.

A listing of subjects for whom the treatment blind was broken during the study, along with the reason, will be produced.

Study drug exposure (in days) is number of days between (double-blind) treatment start date and (double-blind) treatment stop date, both days inclusive. Study drug exposure is further explained in [Appendix 6](#). Study drug exposure in days will be summarized by treatment group and overall. The number and proportion of subjects exposed to study drug will also be summarized by 180-day intervals for each treatment group and overall.

Overall study drug compliance is defined as $100 * \text{Number of Pills Consumed} / \text{Number of Pills Prescribed}$. Compliance for a specific study drug component (e.g. Tamsulosin) is defined in the same way. Both of these definitions are explained further in [Appendix 6](#). Overall study drug compliance will be summarized by treatment group and across the treatment groups. The number and proportion of subjects with overall compliance <75%, 75-125%, and >125%, will be summarized for each treatment group and across the treatment groups. Study drug compliance by component will also be summarized by treatment group and across the treatment groups.

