11.1. Appendix 1: Exclusions from the Per-Protocol Population

In accordance with SOP-130050 and the ARI114265 PDMP, deviations which require exclusion from the Per-Protocol population must be identified, when possible, in advance of treatment unblinding. The deviation review and programming processes, as well as spreadsheet and database capabilities, require that deviation identification must be made from two sources:

1. Study Team Assessment of deviations tracked on study team's protocol deviations spreadsheet and then indicated as 'Exclude from Per-Protocol'
- and
2. Programmatic Assessment which outputs deviations through Statistics & Programming electronic SAS code execution.

The below table lists the 19 deviations which would exclude a subject from the Per-Protocol population along with identification methods. It is expected that a final analysis dataset will be generated with the two sources pooled. Details on the pooled dataset programming and any adjudication process required to reconcile the two sources will be defined in advance of database freeze through a RAP amendment or a high level note to Study File. If there is inconsistency between the two sources, it is anticipated that the programmatic determination will be considered definitive; this will be outlined through a RAP amendment or a high level note to Study File.

Number	Per-Protocol Deviation	Study Team Assessment	Programmatic Assessment [eCRF Code Note a]
01	Missed placebo run-in phase	Any evidence which implies or documents that subject missed the placebo run-in phase.	1) Placebo run-in treatment start and stop dates are missing or 2) Placebo run-in tablets consumed = zero [A5]
02	Incorrect study drug (wrong treatment) consumed	Any evidence which confirms that the incorrect container contains other-than-scheduled study treatment.	Treatment consumed (from incorrect dispensed container) unequal to treatment planned in randomization schedule. Note: this can only be determined after study unblinding. [A5]
03	Randomized but did not consume double-blind study drug	Any evidence which confirms that the zero tablets were consumed in double-blind phase	Final nonmissing cumulative study drug compliance = zero [A5]
04	Cumulative study drug compliance <75%	Study team is unable to calculate RAP-defined study drug compliance. Therefore, deviation will be determined based on programmatic	Final nonmissing cumulative study drug compliance < 75% [A5]

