Number	Per-Protocol Deviation	Study Team Assessment	Programmatic Assessment [eCRF Code Note a]
		assessment.	
05	Cumulative study drug compliance >125%	Study team is unable to calculate RAP-defined study drug compliance. Therefore, deviation will be determined based on programmatic assessment.	Final nonmissing cumulative study drug compliance > 125% [A5]
	Violation of Inclusion Criteria (protocol #)		
06	Confirmed BPH clinical diagnosis (Inclusion 2)	Any evidence which confirms inclusion criterion 2 deviation.	Eligibility database indicates violation of inclusion criterion 2 [A1]
07	IPSS \geq 12 at Screening (Inclusion 3)	Any evidence which confirms inclusion criterion 3 deviation.	Eligibility database indicates violation of inclusion criterion 3 [A1]
08	Prostate volume \geq 30cc by TRUS at Screening (Inclusion 4)	Any evidence which confirms inclusion criterion 4 deviation.	Eligibility database indicates violation of inclusion criterion 4 [A1]
09	PSA \geq 1.5ng/ml and \leq 10ng/mL at Screening (Inclusion 5)	Any evidence which confirms inclusion criterion 5 deviation.	Eligibility database indicates violation of inclusion criterion 5 [A1]
10	Qmax $>$ 5 mL/sec and \leq 15mL/sec with Voided Volume \geq 125mL/sec at Screening (Inclusion 6)	Any evidence which confirms inclusion criterion 6 deviation.	Eligibility database indicates violation of inclusion criterion 6 [A1]
	Violation of Exclusion Criteria (protocol #)		
11	Any conditions other than BPH, which may in the judgement of the investigator, result in urinary symptoms or changes in flow rate (Exclusion 6)	Any evidence which confirms exclusion criterion 6 deviation.	Eligibility database indicates violation of exclusion criterion 6 [A1]
12	Use of 5ARI within 6 months of Screening or historical TRUS and throughout the study (Exclusion 10a)	Any evidence which confirms exclusion criterion 10a deviation.	Reference Note b. [A1]
13	Use of anabolic steroids within 6 months of Screening and throughout the study (Exclusion 10b)	Any evidence which confirms exclusion criterion 10b deviation.	Reference Note b. [A1]
14	Use of phytotherapy for BPH within 2 weeks of Screening and throughout the study (Exclusion 10c)	Any evidence which confirms exclusion criterion 10c deviation.	Reference Note b. [A1]

Number	Per-Protocol Deviation	Study Team Assessment	Programmatic Assessment [eCRF Code Note a]

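### Per-Protocol items 04 and 05 appear to use compliance averaged over capsule and tablet, so good tamsulosin intake can mask poor intake of the randomised capsule

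*SAP*

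**What the plan says.** **The rules.** Appendix 1 of the SAP (RAP amendment 01) sets the programmatic test for item 04 as "Final nonmissing cumulative study drug compliance < 75" (per cent) and for item 05 as "Final nonmissing cumulative study drug compliance > 125" (per cent). Both items rest on programming alone, because "Study team is unable to calculate RAP-defined study drug compliance".

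**The definitions.** Appendix 6 defines overall compliance as all pills consumed, as a percentage of twice the exposure days, "since the protocol prescribes that subjects consume 2 pills for each day a subject is on treatment". The two are the dutasteride or placebo capsule and the tamsulosin tablet. It also defines compliance for each component, with one pill per exposure day as the denominator. Exposure runs from the earlier of the two containers' start dates to the later of their stop dates.

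**The use of each figure.** Section 6.6 applies the bands below 75%, 75–125% and above 125% to overall compliance. For the component figure it says only "Study drug compliance by component will also be summarized by treatment group and across the treatment groups". No cut-off and no Per-Protocol item refers to the component figure. The word *cumulative*, used in items 04 and 05, is not defined anywhere in the SAP.

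**The arms.** Both arms take tamsulosin 0.2 mg once daily. They differ only in whether the capsule contains dutasteride or placebo (Sections 1 and 2.3).

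**The concern.** The Per-Protocol set is meant to hold men who adhered closely to the protocol, and its analysis should show the effect in men who took the assigned treatment. Here the randomised contrast lies entirely in the capsule. A figure that averages the capsule with a tablet common to both arms lets one offset the other, so a man clearly short of the plan's own 75% standard on the tested component can be kept because he took his tamsulosin.

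Two things are at stake:

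- Keeping combination-arm men with low dutasteride intake would be expected to dilute the Per-Protocol difference. A Per-Protocol result that agrees with ITT would then say less about adherence to the tested drug than it seems to.
- The Per-Protocol analysis runs only if the set is 80% or less of ITT. Each man kept by the averaging raises that percentage, so the rule also bears on whether the analysis is run at all.

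**Working it through.** The plan states no result on this point to reproduce, so the check applies its formulas directly.

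**Inputs**
- Exposure D = 104 weeks × 7 = 728 days (full treatment period, Section 1).
- Overall compliance = 100 × (capsules + tablets) / (2 × D) (Appendix 6).
- Component compliance = 100 × pills of that component / D (Appendix 6).
- Exclusion if strictly below 75% or strictly above 125% (Appendix 1, items 04 and 05).
- Tablet intake is not given in the SAP. I assume a range of 90–105%.

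**Which figure the rules use.** This is an inference: Section 6.6 puts the same 75% and 125% bands on overall compliance, and nothing links items 04 and 05 to the component figure.

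**General condition.** Write c and t for capsule and tablet compliance in per cent. Overall = (c + t)/2, so a man is kept when 150 ≤ c + t ≤ 250, that is, when c lies between 150 − t and 250 − t.

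| Tablet intake t | Capsule intake kept | Kept if each component had to lie in 75–125% |
|---|---|---|
| 90% | 60–160% | 75–125% |
| 95% | 55–155% | 75–125% |
| 100% | 50–150% | 75–125% |
| 105% | 45–145% | 75–125% |

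**Worked cases**
- 60% capsule, 90% tablet: (60 + 90)/2 = 75.0%, kept. The capsule component is 60%, below the cut-off.
- 60% capsule, 100% tablet: (60 + 100)/2 = 80.0%, kept.
- Half the capsules, every tablet: (364 + 728)/1456 = 75.0%, kept. The capsule component is 364/728 = 50%.
- Half the capsules, one tablet missed: (364 + 727)/1456 = 74.93%, excluded.
- No capsules, every tablet: 728/1456 = 50.0%, excluded.
- 150% capsule, every tablet: (1092 + 728)/1456 = 125.0%, kept. The capsule component is 150%.
- 150% capsule, 95% tablet: (150 + 95)/2 = 122.5%, kept.

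**Early stop of the capsule.** Exposure ends at the later of the two stop dates. A man who stops the capsule halfway but takes every tablet therefore keeps D = 728 and scores 75.0% overall. The component formula uses the same exposure and gives 50%, so it would identify him.

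**The case against.** A reader might infer that any man who takes half his capsules, or none, counts as compliant, and that the rules cannot find capsule under-dosing. The documents do not support that. The 50% and 150% cases with full tablet intake sit exactly on strict cut-offs, and one missed tablet takes the first to 74.93% and exclusion. Capsule intake below half is kept only if tablets are over-consumed. A man who takes no capsules and all his tablets is excluded. If both pills are missed together, the overall and component figures agree. What remains is the range from about 50–60% up to 75% capsule intake, which does not depend on the boundary.

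Other points on the plan's side:

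- *The term is undefined.* Reading *cumulative* as overall is an inference, and the protocol, which is not at hand, called these deviations major and may be the source of the rule. This stands as a limit on certainty. If the component figure was intended, though, the SAP does not say so, and the rule cannot be programmed unambiguously.
- *Item 19.* The study team may exclude a man after reviewing, among other sources, compliance outliers. This is a real safeguard, and item 19 has no programmatic counterpart to override it. But it is discretionary and has no component criterion, so it mitigates the gap without closing it.
- *Consequence.* The primary analysis is ITT with LOCF, and the multiplicity rules rest no decision on the Per-Protocol set. Dilution would not create a false claim of superiority. Component compliance is summarised by arm, so a difference in capsule adherence would still be visible. All of this stands and keeps the point modest.
- *Preference.* The averaged figure is pre-specified and applied alike to both arms. That is true, but it does not measure adherence to the component under test.

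**Conclusion.** The point holds in a limited form. On the natural reading of items 04 and 05, and with tablet intake of 90–100%, men with capsule intake from about 50–60% up to 75% stay in the Per-Protocol set, and capsule intake up to about 150–160% is not flagged under item 05. This rests on two assumptions: that *cumulative* means overall compliance, and that tablet intake lies in the stated range.

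The effect is confined to the supportive Per-Protocol analysis of the primary endpoint and to the 80% condition for running it. The SAP does not give the number of men affected, so neither the dilution nor any change in whether the analysis is triggered can be sized; both are possibilities. It would go too far to conclude that the primary result is at risk, since the ITT analysis does not use compliance at all. The change is worth making because it is cheap and brings the Per-Protocol set into line with its stated purpose.

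**What to change.** In Section 4.1.3 and Appendix 1, items 04 and 05, name the compliance figure that is used. Apply the existing cut-offs of below 75% and above 125% to each component as already defined in Appendix 6, and exclude a man if either the capsule or the tablet component falls outside. In Section 6.6 and Table 1.32, report the three compliance bands by component as well as overall.

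This keeps the plan's own cut-offs, uses variables already derived, and needs only a few lines of text and code. The cost is a somewhat smaller Per-Protocol set, including some tamsulosin-arm men excluded for missed placebo capsules, and therefore a somewhat greater chance that the Per-Protocol analysis is triggered. The primary analysis does not change.

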11.7. Appendix 7: Premature Withdrawals & Handling of Missing Data

11.7.1. Premature Withdrawals

Element	Reporting Detail
General	
 Subject study completion (i.e. as specified in the protocol) is defined as completion of the 4-week placebo run-in and the 104-week study treatment period. Withdrawn subjects will not be replaced in the study. All available data from subjects who were withdrawn from the study will be listed and all available planned data will be included in summary tables and figures, unless otherwise specified. Number and percent of ITT population completing the study and those withdrawing from the study, along with eCRF recorded reasons for premature withdrawals, will be summarized by treatment and overall.
Note	This section addresses Premature Withdrawals from the study. Premature discontinuation of investigational product, along with reasons, is a separate data collection and is reported separately.

11.7.2. Handling of Missing Data

11.7.2.1. Handling of Missing or Partial Dates

For efficacy time to event endpoints, such as 'Time to AUR or BPH-Related Surgery' the following approach will be used for unknown event dates unless otherwise indicated. If the month and year are known but the day of the month is unknown, then the day of the month will be imputed to be the 15th. If the year is known but the month and day are unknown then the date will be imputed to be July 2 in that year. In all the preceding cases, if it is not definitive that the onset date is on or after the treatment start date based on the non-missing (non-imputed) dates, then the date will be imputed to be the treatment start date. If the year is unknown then the onset date is considered to be prior to treatment start; hence, the event will be excluded from summaries of events on or after treatment start. For subjects without events, the censoring dates will be established using non-missing dates, and using dates with only days missing. Dates with missing months and years will not be used in establishing the censoring dates.

Partial adverse event dates will be handled as described in Appendix 8.

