8.1.5. AUR or BPH-Related Surgical Intervention

All AUR and BPH-related surgery events during participation in the study are recorded. Subjects who discontinue from the study are followed for AUR and BPH-related surgery until the 24 month anniversary of randomization. This follow-up is in terms of biannual telephone contacts beginning at the first six month scheduled interval after discontinuation. Analyses will be in terms of events recorded at clinic visits and also collected in the biannual telephone contacts. [Table 4](#) provides an overview of the planned summaries and analyses. A list of planned data displays is in [Appendix 15](#): List of Data Displays.

Time to first AUR or BPH-related surgery will be defined as the number of days from treatment start date to date of the first event (earliest occurring of either AUR or BPH-related surgery) for each subject. Time to first AUR or BPH-related surgery is classified as a secondary efficacy endpoint and will be analyzed in terms of the Intent-to-Treat population.

Censoring will occur at the earliest of the following dates as applicable: the date of prostatectomy, the date of last contact for AUR and surgical intervention, and the date of death. For censoring, 'prostatectomy' will be determined from the eCRF prostatic surgical intervention log using the following codes associated with 'prostatectomy': open, retropubic with or without nerve-sparing, suprapubic, transvesical, perineal, salvage, laparoscopic, laparoscopic assisted. Note this excludes 'partial prostatectomy'.

The 'date of last contact for AUR and surgical intervention assessment' will be assigned as the latest of:

- Date of last treatment-phase visit
- and
- Date of last successful biannual follow-up telephone contact.

Partial dates will be handled as described in Appendix 7, Premature Withdrawals & Handling of Missing Data.

The number of subjects having the first AUR or BPH-related surgery event on or after treatment start will be tabulated by treatment, by the two annual time periods (Month 12 and Month 24), as well as by three month intervals (quarterly) along with the number of subjects at risk during each of these time periods.

Note: Cut-off dates are defined in [Appendix 6](#); definition is repeated here:

Month k Cut-off Date (for k= 3, 6, 9, 12, 15, 18, 21, 24): The maximum of [Month k clinic visit date, Month k lab visit date, Baseline Date + (k * 91/3)].

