The primary analysis of this endpoint will compare combination treatment versus tamsulosin treatment in terms of time to first AUR or BPH-related surgery for the ITT population using a log rank test stratified by cluster at the 0.05 level of significance. The relative risk (hazard ratio) for the treatment effect and associated two-sided 95% confidence intervals will be estimated using a Cox proportional hazards model with treatment as the only covariate and stratified by cluster. Estimates and corresponding confidence intervals for the relative risk (hazard ratio) and risk reduction (1-hazard ratio) of combination treatment versus tamsulosin treatment will be presented along with the log rank p-value. Assessment of the Cox modeling procedure will include examination of diagnostic plots to assess the assumption of proportional hazards and the review of results obtained by fitting separate models by cluster to assess the homogeneity of treatment effect across clusters.

Time to first AUR or BPH-related surgery, expressed as months, will be summarized by treatment group for the ITT population using product-limit estimates computed by the Kaplan-Meier method and displayed graphically as Kaplan-Meier curves.

The number of subjects with at least one AUR or BPH-related surgery will be summarized by treatment group across the 2 year period. The crude rate of AUR or BPH-related surgery incidence will be calculated using the Intent-to-Treat population of each treatment as the denominator; the associated 95% confidence interval will be output. This crude rate will be compared for combination treatment versus tamsulosin treatment using the Mantel-Haenszel test stratified by cluster at the 0.05 level of significance.

AUR or BPH-related surgery event details per subject will be summarized by treatment and will include: event component (first occurring of either AUR or BPH-related surgery) and time period of first occurring event (during treatment or after treatment stop). BPH-relatedness (yes/no) and AUR precipitating factors will be summarized by treatment for subjects in which AUR is the primary efficacy event's initial component. Types of surgery/intervention will be summarized by treatment for subjects in which BPH-related surgery is the primary efficacy event's initial component.

Time from last dose to first AUR or BPH-related surgery event will be summarized for those subjects experiencing the first event after treatment stop.

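### The partial-date rule for AUR and BPH-related surgery excludes unknown-year events and dates start-year, year-only events to day 0, even when first recorded after Visit 2

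*SAP*

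**What the plan says.** SAP 8.1.5 defines the endpoint as "the number of days from treatment start date to date of the first event". It takes events from clinic visits and from calls after discontinuation: "This follow-up is in terms of biannual telephone contacts beginning at the first six month scheduled interval after discontinuation". It then refers date handling onward without exception: "Partial dates will be handled as described in Appendix 7".

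Appendix 7 (11.7.2.1) gives these rules for AUR and surgery:
- **Day missing:** the 15th of the month.
- **Year only:** "then the date will be imputed to be July 2 in that year".
- **Override of both:** "if it is not definitive that the onset date is on or after the treatment start date", judged on the recorded date parts alone, "then the date will be imputed to be the treatment start date".
- **Year missing:** "If the year is unknown then the onset date is considered to be prior to treatment start; hence, the event will be excluded". This exclusion applies to the on- or after-treatment tabulations.

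The Time and Events table (Appendix 2) marks AUR and surgery for collection from Visit 2 onward. For adverse events, Appendix 8 (11.8) counts a missing onset date as On Treatment. A partial date that cannot be placed clearly before the start or after the stop of treatment is also On-Treatment.

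**The concern.** An event first recorded at Visit 3 or later, or at a biannual call, has a latest possible date: the contact that recorded it. Where the previous contact is documented as event-free, it has an earliest date too. Appendix 7 uses neither. An unknown-year event picked up well into follow-up is therefore presumed to pre-date treatment. A start-year event with only the year known is placed on day 0, possibly ahead of visits at which the man had no event. The 2 July default can fall after the contact that reported the event.

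AUR and BPH-related surgery are the clinical outcomes named in the secondary objective (SAP 2.2). Excluding an event affects the stratified log-rank test, the Cox hazard ratio, the Kaplan-Meier curves and the crude-rate Mantel-Haenszel comparison. Moving an event affects only the outputs that use time: log-rank, Cox, Kaplan-Meier, the quarterly table, the during- or after-treatment split, and the interval described here: "Time from last dose to first AUR or BPH-related surgery event will be summarized for those subjects experiencing the first event after treatment stop".

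**Working it through.** The SAP states no sample size, event count, power or partial-date frequency for this endpoint, so there is no figure to reproduce. The rule was applied literally to test dates.

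**1. Output of the rule.** Assume first dose on 10 March 2014.

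| Recorded date | Result under Appendix 7 |
|---|---|
| Year unknown | Excluded, whichever contact recorded it |
| 2014 only | Day 0 |
| March 2014, day missing | Day 0 |
| November 2014, day missing | Day 250 (15 November) |
| 2015 only | Day 479 (2 July 2015) |
| 2013 only | Day 0, read literally |

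A surgery on 20 December 2014 is truly day 285. Recorded as 2014 only, it becomes day 0. An event recorded as 2015 only but reported at a contact in March 2015 is dated 2 July, after its own report. The last row is probably unintended: a year before the start year is also not certain to be on or after start, so the override makes a known pre-treatment event count on day 0.

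**2. When the override applies.** If the known year is the start year, that year contains days before first dose unless first dose was on 1 January. The year alone then never settles the matter, and the override always applies.

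**3. Size of the shift for start-year, year-only events.** Let L be the days left in the start year, from 1 to n = 365. Assume uniform start dates and a constant hazard, so the mean shift for a given L is L/2.
- Weighted by time at risk: Σ(L²/2)/ΣL = (2n + 1)/6 = 731/6 ≈ 122 days.
- Equal weight per start date: (n + 1)/4 = 366/4 = 91.5 days.
- Maximum: 2 January to 31 December, which is 363 days, or 364 in a leap year.
- Share of follow-up in the start year: mean L = 183, and 183/728 ≈ 25%.

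**4. What contact dates would give.** Scheduled visits are 13 weeks (91 days) apart, so a midpoint is at most 91/2 = 45.5 days off. Six-monthly calls (about 182 days) give at most 91 days. Take the same surgery on day 285, and assume an event-free Month 9 visit on day 273 and first report at Month 12 on day 364.
- Year unknown: midpoint (273 + 364)/2 = 318.5, so the event is kept and is 33.5 days late.
- Year 2014 known: the upper bound becomes 31 December (day 296), and the midpoint is (273 + 296)/2 = 284.5.

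**5. Sensitivity to lost events (assumed counts).** With 10 versus 20 events in equal arms the rate ratio is 0.50.
- Losing 1 or 2 combination events: 9/20 = 0.45 or 8/20 = 0.40.
- Losing 1 or 2 tamsulosin events: 10/19 = 0.53 or 10/18 = 0.56.

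With 20 to 80 events and hazard ratios of 0.4 to 0.6 (Schoenfeld formula, two-sided 0.05, 1:1), losing 1 or 2 events lowers power by about 0.1 to 4 percentage points.

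**The case against.** The strongest reply is that this is a fallback for rare residual cases on a secondary endpoint. AUR and surgery seldom lack a year, and SAP 3.2 requires database cleaning before freeze, so a missing year can be queried. The rule is pre-specified and identical in both arms. The 15th and 2 July are ordinary mid-period conventions. All of that stands and limits the weight of the point, but it does not make the default right for events known to have been first recorded after Visit 2.

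The documents do not support several stronger readings that a reader might infer:
- **That the events are deleted.** SAP 8.1.5 still lists all AUR and surgery data; the exclusion is from analysis. How such a man is then censored is not stated.
- **That every affected event is shown to be post-treatment.** Collection starts at Visit 2, and an event recorded there may truly pre-date treatment.
- **That poorly dated events cluster among withdrawn men followed by telephone.** This is plausible, but the SAP has no information on it.
- **That the crude-rate test is distorted throughout.** A re-dated event still counts there; only the unknown-year exclusion affects it.

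The SAP also does not show that an event-free answer is stored at every contact, or that each event record carries its reporting contact. The fix must allow for that.

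**Conclusion.** The point holds and is minor. Followed as written, Appendix 7 presumes pre-treatment onset for events whose first recording may show otherwise, assigns day 0 to start-year events with only the year known, and can date an event after its own report. It also runs against the default that the same SAP uses for adverse events. The wording in 11.7.2.1 that leaves room for exceptions does not help, because 8.1.5 makes none.

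The total effect is unknown. The shift sizes rest on uniform starts and constant hazard, and the rate-ratio and power figures on assumed event counts. The number of affected events is probably small. Nothing in the SAP shows a bias favouring either arm, or that the endpoint's conclusion would change.

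**What to change.** Amend 11.7.2.1 for AUR and BPH-related surgery:

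1. Count any event first recorded after Visit 2 as on or after treatment start, unless its known date parts place it before treatment start.
2. Impute missing date parts as the midpoint of the allowed interval, restricted to the known month or year. The lower bound is the later of treatment start and the last event-free contact, where one is recorded. The upper bound is the reporting contact or death, whichever is earlier.
3. Leave events recorded at Visit 2 under the existing rule.

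The cost is a paragraph of SAP text and a small change to one derivation, with no new data collection. Visit dates are already listed (SAP 6.3), as are the telephone contacts (Listing 2.5). The change depends on linking each event record to the contact that reported it, which should be confirmed against the database structure first.
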